8.4. Security Visit

4 weeks after the end of treatment for any reason, the safety visit will be carried out, during which the following will be carried out:

- Physical examination, and vital signs (resting pulse measurements, blood pressure, respiratory rate, temperature, weight, and height).
- ECOG (Eastern Cooperative Oncology Group) functional status
- Barthel index
- Minimental Test
- Analytical tests:
 - Complete blood count including a total white blood cell count with differential, hemoglobin, and platelet count.
 - Serum biochemistry including creatinine, total bilirubin, alkaline phosphatase, aspartate aminotransferase (AST) or SGOT, alanine aminotransferase (ALT) or SGPT.
- Systematic urine analysis
- Registry of adverse events

MRI imaging tests will be performed every 12 weeks until disease progression, responses to treatment (PR, CR) must be confirmed at 4 weeks using the same method, if the patient abandons treatment for any reason before progression. , MRIs should continue to be performed every 12 weeks as part of the follow-up until progression.

8.5. Follow-up visits from the end of treatment without progression to PE

Once treatment is completed for any cause other than disease progression, the following procedures will be performed every 6 weeks until disease progression:

- Physical examination, and vital signs (resting pulse measurements, blood pressure, respiratory rate, temperature).
- ECOG (Eastern Cooperative Oncology Group) functional status
- Barthel index
- Minimental Test
- Analytical tests:
 - Complete blood count including a total white blood cell count with differential, hemoglobin, and platelet count.
 - Serum biochemistry including creatinine, total bilirubin, alkaline phosphatase, aspartate aminotransferase (AST) or SGOT, alanine aminotransferase (ALT) or SGPT
- Systematic urine analysis
- Radiological images in localization of the disease using MRI. Cranial MRI that will be taken as a base scan in terms of response scan. The response should always be assessed with the same equipment as the baseline MRI.

8.6. Post-progression follow-up

Once the patient progresses, follow-up for overall survival until death every 4 weeks, which can be either visits to the oncology service or telephone calls. The patient's current status and registration of new cancer treatments will be determined.

The date of death will be verified to determine survival.

8.7. Response evaluation

The evaluation of the response will be carried out in each center using the radiological results, the patient's symptoms and the doses of dexamethasone required. It will be based on the recently modified RANO response criteria. The RANO criteria will be followed for the global assessment of response. In the progression due to sudden neurological deterioration, it is advisable to perform a radiological examination. If the radiological examination cannot be performed, progression of brain disease will be considered.

Imaging tests (MRIs) will be performed every 12 weeks until disease progression. Responses to treatment (PR, CR) must be confirmed at 4 weeks using the same method, as required by the RANO criteria. If the patient discontinues treatment for any reason before progression, MRIs should continue to be performed every 12 weeks as part of the follow-up until progression.

Once the patient progresses, follow-up for overall survival will be done until death, every 4 weeks. It can be both visits to the oncology service and telephone calls. The patient's current status and registration of new cancer treatments will be determined.

9. ADVERSE EVENTS

Timely, accurate and complete communication and analysis of safety information from clinical studies is crucial for the protection of patients, investigators and the sponsor, and is a requirement enforced by regulatory agencies around the world. The sponsor has established standard operating procedures (SOPs) in accordance with international regulatory provisions to ensure proper communication of safety information; All clinical studies conducted by the sponsor or its affiliates will be conducted in accordance with these procedures.

9.1. Definition

Adverse event (AA):

An AE is any unfavorable medical incident in a patient or subject of a clinical investigation, even if it does not necessarily have a causal relationship with the study treatment. Any event involving adverse reactions to the drug, illnesses that begin during the study, or exacerbations of preexisting illnesses should be recorded.

In addition, clinically important abnormalities found on physical examination and abnormal findings on objective tests (e.g., x-rays or ECG) should also be recorded as AEs. The

Criteria for determining whether an abnormal objective test finding should be reported as an AE are as follows:

- the test result is associated with clinically important symptoms, and/or
- the test result leads to a change in study treatment or withdrawal of the patient from the study, significant additional concomitant drug or other treatment, and/or
- the test result leads to one of the outcomes indicated in the definition of AAG, and/or
- the investigator considers the test result to be an AA.

Serious adverse event (SAE):

An SAE is any adverse event occurring with any dose that:

- produces death (is fatal),
- threatens the patient's life,
- makes hospitalization or prolonged hospitalization necessary,
- produces persistent or significant disability or disability,
- is a congenital anomaly or birth defect, or
- is medically important.

Medical and scientific judgment should be exercised to decide whether urgent communication is appropriate in other situations, such as important medical events that do not immediately threaten the patient's life or lead to hospitalization but may endanger the patient or may require intervention to prevent one of the outcomes listed in the definition above.

Any suspected transmission of an infectious agent through a medication is also considered a serious adverse reaction.

Life-threatening event:

Any event in which the patient is at risk of death at the time of the event; It does not refer to an event that hypothetically could have caused death if it had been more severe.

Hospitalization/prolongation of hospitalization:

Any event requiring hospitalization (or prolonged hospitalization) that occurs or worsens during a patient's participation in a clinical study should be reported as an SAE. Prolongation of hospitalization is defined as any extension of a patient's hospitalization beyond the planned/required stay at initial admission, in the judgment of the investigator or the doctor responsible for the patient.

The following hospitalization cases do not meet the SAE reporting criteria:

- a) Reasons described in the protocol (for example, drug administration, complementary tests required by the protocol). Hospitalizations or prolongations of hospitalization due to a complication of the administration of treatment or procedures will be reported as SAEs.
- b) Hospitalizations or extensions of hospitalization for technical, practical or social reasons, in the absence of an AA.
- c) Previously scheduled hospitalizations (that is, scheduled before entry into the study). Any surgical intervention or procedure scheduled prior to study entry must be documented in the CRD.

Unexpected adverse event (not listed):

An unexpected AE, the nature or severity of which does not correspond to the information regarding the product.

The reference document to establish expectability will be the current version of the palbociclib investigator's manual.

Associated with drug use

An AE is considered associated with the use of the investigational medicinal product if the causality assessment is related to one of the investigational medicinal products or is unknown according to the definitions below.

Causality assessment

The investigator must provide a causality assessment for each investigational medicinal product (including combination products and comparators) according to the following criteria:

AND There is a reasonable possibility that the study medication(s) will cause the serious adverse event.

N There is no reasonable possibility that the study medication(s) will cause the serious adverse event and other causes are more likely.

UK Unknown. It should only be used in special situations where the researcher has insufficient information (for example, the patient has not been treated at your center), and if none of the previous options can be used.

Urgent communication

The promoter will assume responsibility for the proper communication of AAs to the regulatory authorities. The sponsor will also report all unexpected SAEs associated with the use of the study treatment to the investigators

and clinical research ethics committees (CEIC) in accordance with current regulations, unless other measures are required and documented by the CEIC. .

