4.4.4. Clinical experience with Palbociclib in humans

In addition to the phase 1 study with increasing doses (A5481001), there are others evaluating tolerance and activity of the compound in different tumors. The second study launched with Palbociclib (A5481002) is evaluating the pharmacodynamics, clinical activity and safety of PD 0332991 in patients with previously treated mantle cell lymphoma. PD 0332991 is being administered according to the 3/1 schedule at a dose of 125 mg once daily. 17 patients have been included in the study. One complete response and two partial responses were observed. The safety profile has been similar to that observed in the study with increasing doses.

Another study (A5481004) is aimed at evaluating the safety and clinical activity of PD 0332991 in combination with bortezomib and dexamethasone in patients with refractory multiple myeloma.

The A5481003 clinical trial is the first phase 2 study in which we have information on the activity of the drug in a specific tumor, in this case metastatic Her2-negative, hormone receptor-positive breast cancer. In these patients, Palbociclib has shown an important and significant increase in Progression-Free Survival (PFS) when associated with letrozole compared to treatment with letrozole as monotherapy (20.2 months for the combination versus 10.2 months).¹. The combination was well tolerated when compared to treatment with letrozole monotherapy. The most common side effects of the combination were uncomplicated neutropenia, leukopenia and asthenia and the most common Grade 3 side effect was neutropenia (54%) and leukopenia (21%). The most common Grade 4 side effect was neutropenia and asthenia, 6% each. Only 9% of patients in this trial who received Palbociclib had to stop treatment. Given the promising data from this phase II clinical trial, study A5481008 has recently been launched to compare the efficacy of letrozole + Palbociclib versus letrozole in patients with ER+HER2- metastatic breast cancer in an extensive randomized phase III.

In brain tumors, a study has already been launched (NCT01227434) that evaluates the activity and safety of the drug in recurrent glioblastoma and also associates a pharmacokinetic and pharmacodynamic study in samples of glioblastoma operated on days after the start of treatment with the drug.

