4.6.2. Secondary objectives

- To evaluate the safety and tolerability of oral administration of Palbociclib in patients with recurrent anaplastic oligodendrogliomas.
- Evaluate the antitumor response according to the RANO criteria
- Assess Global Survival (GS)
- To evaluate the duration of response in patients with an objective response.
- Assess changes in glucocorticoid use.
- Assess changes in neurological status
- To evaluate whether the following biomarkers are related to PFS and OS: deletions in CDKN2A, deletions in CDKN2B, CDK4 amplification, CDK6 amplification, cyclin D amplification.
- To evaluate whether the following biomarkers are related to the response rate: deletions in CDKN2A, CDKN2B deletions, CDK4 amplification, CDK6 amplification, Cyclin D amplification.

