Coagulation tests: Coagulation studies will include prothrombin time (PT), partial thromboplastin time (PTT), and fibrinogen.

ECG: An electrocardiogram (ECG) value must be obtained at baseline, within 28 days before inclusion, and every 8 weeks thereafter.

Pregnancy test: Serum or urine pregnancy test for women of childbearing age.

Cranial Magnetic Resonance: Cranial MRI that will be taken as a base examination in terms of response evaluation (it is allowed to be performed in a period ≤ 28 days). The response should always be assessed with the same equipment as the initial examination. If the corticosteroid dose increases after the cranial MRI and the start of treatment, a new baseline MRI should be performed. That is, at the time of starting treatment, the dose of corticosteroids must be equal to or less than the dose that the patient was taking at the time of the MRI used as baseline.

Response evaluation will follow the RANO and McDonald criteria for brain lesions visualized on MRI.

Send tumor sample: Submission of tumor for centralized review to confirm the diagnosis of Anaplastic Oligodendroglioma (OA) in a central neuropathology laboratory. It will also be determined if there is nuclear expression of the RB protein by Immunohistochemistry.

Palbociclib Dispensing: Palbociclib capsules will be dispensed for 21-day treatment periods.

Therapeutic compliance: Any missed dose or loss due to vomiting should be indicated in the patient's diary, medical history and CRD, in the same way as all doses administered.

Corticosteroid dosage: Record in the patient's medical history and in the CRD the doses of corticosteroids for the 5 days prior to inclusion. At each visit, the dose of corticosteroid received by the patient must be recorded in the clinical history and in the CRD.

Toxicities record: Safety assessments and adverse events include tumor-related, treatment-related, and unrelated signs and symptoms. Adverse events will be documented and recorded in the CRD upon notification by patients. Specific questions will be asked about adverse events. Adverse events will be monitored at the post-treatment follow-up visit 30+/-3 days after the end of treatment or until all drug-related toxicities have resolved or are considered irreversible, whichever occurs later. Toxicity grading will be based on the National Cancer Institute Common Terminology Criteria for Adverse Events, version 4.0 (NCI CTCAE v4.0).

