1.2.2. ADEVERSE EVENTS

The most frequent adverse event (any grade) were xxxxx (xx%, n=xx)....

Table 43. Frequencies of all adverse events

Adverse event	N	%
EXAMPLES:		
Neutrophil count decreased		
Fatigue		
Platelet count decreased		
Anaemia		
.....		

%: calculated respect the total number of patients (N=34)

The most frequent adverse events, (at least in 10% of the patients, n=xx), are reported in the following table:

Table 44. Most frequent adverse events

	N	%	
Specify Adverse events.	No	10	29.4%
	Yes	24	70.6%
EXAMPLE: Fatigue	Total	34	100.0%
.....	No	14	41.2%
	Yes	20	58.8%

Total	34	100.0%
--------------	----	--------

The most frequent adverse events with their respective grades are reported in the following table:

Table 45. Most frequent adverse events with grades

	No		G1		G2		G3		G4		Total	
	N	%	N	%	N	%	N	%	N	%	N	%

Specify Adverse events.

EXAMPLE: Fatigue

.....

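### Silent laboratory and QTc abnormalities need not be recorded as adverse events, and the SAP has no on-treatment laboratory or QTc table, so some toxicity rates may be under-ascertained to an unknown extent

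*Protocol*

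**What the plan says.** The first secondary objective in protocol 4.6.2 is "To evaluate the safety and tolerability of oral administration of Palbociclib in patients with recurrent anaplastic oligodendrogliomas".

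**What becomes an adverse event.** Protocol 9.1 sets the rule with "Criteria for determining whether an abnormal objective test finding should be reported as an AE are as follows". The first criterion is "the test result is associated with clinically important symptoms, and/or". The second begins "the test result leads to a change in study treatment or withdrawal of the patient from the study" and extends to significant added medication or other treatment. The third is an outcome listed in the definition of a serious event. The fourth is that the investigator considers the result an adverse event. On the route into the CRD, 8.1 states "Adverse events will be documented and recorded in the CRD upon notification by patients" and adds that patients will be asked specific questions.

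**What is measured.** Under 8.3, blood counts with differential and chemistry are taken at each treatment visit: day 1 and mid-cycle in cycles 1 and 2, then day 1 of each later cycle. For ECG, 8.1 states "An electrocardiogram (ECG) value must be obtained at baseline, within 28 days before inclusion, and every 8 weeks thereafter".

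**What is tabulated.** Haematology, chemistry, coagulation and QTc appear in SAP Tables 8, 9, 10 and 12 (numbering as in the body of the SAP), all under the baseline heading of 1.1.2. On-treatment laboratory findings appear only as adverse event terms in Tables 43 to 48. For example, the SAP announces "The most frequent adverse events with their respective grades are reported in the following table", with columns for G1 to G4. The SAP uses toxicity to mean a related adverse event.

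**The concern.** Myelosuppression is the drug's main toxicity in the protocol's own account: 4.4.3 reports that all dose-limiting toxicities in the phase 1 study were of this kind. It is usually seen first in a blood count, not as a complaint. The example terms in SAP Table 43 include reduced neutrophils, reduced platelets and anaemia, so laboratory toxicity is meant to be read from those tables.

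If entry to the log is optional for silent findings, the any-grade and low-grade rates depend partly on how each investigator uses that option, and may differ between sites. The measured values would remove this dependence, but the SAP never analyses them after baseline. The same holds for QTc. Protocol 4.4.2 reports QT prolongation in dogs, and 7.4 contains QTc rules. Yet the only QTc table is a baseline one whose bands stop at 480 msec, the eligibility limit, so it could not display on-treatment prolongation.

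**Working it through.** **The plan's own figures.** The example counts left in SAP Table 44 use a denominator of 34 and reproduce: 24/34 = 70.6%, 10/34 = 29.4%, 20/34 = 58.8%, 14/34 = 41.2%. The rows are marked as examples and cannot be tied with certainty to a laboratory term, so they say nothing about completeness.

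**Which abnormalities reach the log through a treatment change.** Setting 7.4.1 (interruption) and 7.4.2 (restart or new cycle) against the second criterion of 9.1:

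| Finding | Does 7.4.1 or 7.4.2 require action? | Route into the log if silent |
|---|---|---|
| Neutrophils <1,000/mm3 | Yes | Second criterion |
| Platelets <25,000/mm3 | Yes | Second criterion |
| Non-haematological grade ≥3, including chemistry | Yes | Second criterion |
| QTc ≥501 msec (on at least two ECGs in 7.4.1) | Yes | Second criterion |
| Platelets 25,000-50,000/mm3, day 1 | Yes; cycle start needs ≥50,000 | Second criterion |
| Platelets 25,000-50,000/mm3, mid-cycle | No | Discretion |
| Milder neutropenia | No | Discretion |
| Anaemia, leukopenia, lymphopenia, any grade | No | Discretion, unless treated |
| Lower-grade chemistry change | No | Discretion |
| QTc below 501 msec | No interruption; grade 2 has management steps in 7.4.3 | Mostly discretion |

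The severe findings are largely covered. The lower part of the table is not.

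**Whether another SAP table fills the gap.** None does. There is no worst-grade, shift or by-visit table for laboratory values or QTc. The SAP does give by-visit tables and comparisons with baseline for the Mini-Mental test (Tables 36 to 38) and the Barthel index (Tables 39 to 41), so it does not avoid longitudinal tables in general.

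**Illustration of size, not an estimate.** Expected reported rate = true rate × capture probability. The documents give no capture probability, so a range is assumed. Protocol 4.4.4 gives grade 3 rates of 21% for leukopenia and 54% for neutropenia with palbociclib plus letrozole in breast cancer. Applying them to 34 patients is a further assumption.

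- Leukopenia, no action rule: 0.21 × 34 = 7.1 patients. At 75% capture the reported rate is 0.21 × 0.75 = 15.8% (5.4 patients); at 50%, 10.5% (3.6); at 25%, about 5.2% (1.8).
- Neutropenia, action rule applies: 0.54 × 34 = 18.4 patients. Capture should be near 100%; even at 90% the reported rate is 0.54 × 0.90 = 48.6% (16.5 patients).

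Under these assumptions the leukopenia shortfall runs from about 5 points (21.0 − 15.8) to about 16 (21.0 − 5.2). That range reflects only the capture values chosen.

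**The case against.** The strongest reply is that the protocol does not shut these findings out. Section 9.1 opens by saying that abnormal objective tests, ECG included, should be recorded, and its fourth criterion lets an investigator record any result. Section 8.1 adds specific questioning, and 8.3 places laboratory tests and the adverse event registry at the same visits. The SAP's example terms show that laboratory findings were expected in the log. This stands. A reader might infer that the rule excludes silent abnormalities; the documents support only that it does not require them.

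Second, the toxicity that matters most is captured, because neutrophils below 1,000/mm3 oblige an interruption or delay. This also stands, so the concern does not reach grade 3-4 neutropenia.

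Third, a reader might infer that a QTc signal below the interruption threshold would go unseen. That goes too far: 7.4.3 sets out closer monitoring, treatment of reversible causes and specialist consultation for grade 2 prolongation, any of which may lead to an entry. What is missing is a systematic summary.

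Fourth, measured grades have limits. They carry no causality, and after cycle 2 scheduled counts fall only on day 1, after the rest week. The tests are local, and the documents do not show that on-treatment values enter the CRD. These points shape the fix but do not remove the need for it.

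Finally, this is a small single-arm pilot with descriptive safety. That limits the weight of the point, but safety is still a stated objective.

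**Conclusion.** The point holds in limited form. Recording of silent laboratory and ECG abnormalities that need no action is left to the investigator, and the SAP does not use the measured values after baseline. Any-grade laboratory rates, and some grade 3 rates such as leukopenia or anaemia, may be under-ascertained. Low is the plausible direction, but the documents hold neither a capture rate nor on-treatment values. A reader might therefore infer that the toxicity rates are biased low by a known amount, or across the board; neither is supported. Neutrophils below 1,000/mm3, platelets below 25,000/mm3, non-haematological toxicity of grade 3 or more and QTc of 501 msec or more should largely be captured.

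The conclusion assumes that Tables 43 to 48 draw on the CRD adverse event pages. This is inferred from the SAP's use of toxicity for a related adverse event, as the SAP names no data source. The primary endpoint is not affected. The change should be made because it is cheap and replaces discretionary ascertainment with measurement.

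**What to change.** Leave the adverse event and related-toxicity tables unchanged, and add two tables to the SAP beside them:

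1. Worst post-baseline CTCAE v4.0 grade per patient, with shift from baseline, from measured neutrophils, leukocytes, lymphocytes, platelets, haemoglobin, AST, ALT, bilirubin and creatinine.
2. Maximum post-baseline QTc per patient in bands that follow the protocol's thresholds: ≤480, 481-500 and ≥501 msec.

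First confirm that on-treatment values are in the CRD; the SAP gives the database as closed on 10-10-2019. If they are not, say so and state that the laboratory rates depend on investigator reporting.

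Footnotes should state that measured grades imply no causality, and that scheduled counts after cycle 2 fall on day 1, following the rest week, so mid-cycle lows can still be missed.

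If the data are held, the cost is two programmed tables and no new patient procedure. Reported low-grade rates will be higher than those from the adverse event log alone, and the two sources will need to be read together.
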